Non-Interventional Study (NIS) Protocol

Document Number:	N/A
BI Study Number:	1484.0014
BI Investigational Product(s):	N/A
Title:	Characterization of patients with Geographic Atrophy (GA) in the US
Brief lay title:	Patients with Geographic Atrophy and their patient journey in the US
Protocol version identifier:	V1.0
Date of last version of protocol:	04-05-2023
PASS:	No
EU PAS register number:	N/A
Active substance:	N/A
Medicinal product:	N/A
Product reference:	N/A
Procedure number:	N/A
Marketing authorisation holder(s):	N/A
Joint PASS:	NO
Research question and objectives:	To describe and quantify patients with a GA diagnosis in at least one eye, and the progression to wAMD (including how many receive Anti-Vascular Endothelial Growth Factor (Anti-VEGF) treatment) in both eyes and the progression to GA (in the fellow eye).
Country(-ies) of study:	United States of America

BOEHRINGER INGELHEIM Group of Companies

NIS Protocol Template

Page 2 of 30

Study number: 1484.0014

Document number: <insert>

Author/Contact person:	
Phone:	
Email:	
Marketing authorisation holder(s):	N/A
In case of PASS, add: MAH contact person:	N/A
In case of PASS, add: EU-QPPV:	N/A
In case of PASS, add: Signature of EU-QPPV:	N/A
Date:	
Page 1 of 30	
Proprietary confidential information © 2023 Boehringer Ingelheim Group of companies. All rights reserved. This document may not - in full or in part - be passed on, reproduced, published or otherwise used without prior written permission	

BOEHRINGER INGELHEIM Group of Companies**NIS Protocol Template****Study number: 1484.0014****Page 3 of 30****Document number: <insert>****1. TABLE OF CONTENTS**

.....	1
1. TABLE OF CONTENTS.....	3
2. LIST OF ABBREVIATIONS.....	5
3. RESPONSIBLE PARTIES.....	6
4. ABSTRACT.....	7
5. AMENDMENTS AND UPDATES.....	9
6. MILESTONES.....	10
7. RATIONALE AND BACKGROUND.....	10
8. RESEARCH QUESTION AND OBJECTIVES	11
9. RESEARCH METHODS	11
9.1 STUDY DESIGN.....	11
9.1.1 Study population	12
9.2 SETTING	14
9.2.1 Study sites	14
9.2.2 Study visits	15
9.2.3 Study discontinuation.....	15
9.3 VARIABLES	15
9.3.1 Exposures	15
9.3.2 Outcomes.....	16
9.3.2.1 Primary outcomes.....	16
9.3.2.2 Secondary outcomes.....	18
9.3.3 Covariates.....	18
9.4 DATA SOURCES.....	20
9.5 STUDY SIZE	21
9.6 DATA MANAGEMENT.....	21
9.7 DATA ANALYSIS.....	22
9.7.1 Main analysis.....	22
9.7.3 Safety Analysis.....	26
9.8 QUALITY CONTROL	26
9.9 LIMITATIONS OF THE RESEARCH METHODS.....	26
9.10 OTHER ASPECTS	27

GA	Geographic Atrophy
eCNV	Exudative choroidal neovascularization

BOEHRINGER INGELHEIM Group of Companies

[figure not shown]
NIS Protocol Template

Study number: 1484.0014

[figure not shown]
Page 6 of 30

Document number: <insert>

3. RESPONSIBLE PARTIES

Associate [REDACTED] of Ophthalmology

BOEHRINGER INGELHEIM Group of Companies**NIS Protocol Template****Study number: 1484.0014****Page 7 of 30****Document number: <insert>****4. ABSTRACT**

Name of company:	Boehringer Ingelheim
Name of finished medicinal product:	NA
Name of active ingredient:	NA

BOEHRINGER INGELHEIM Group of Companies

NIS Protocol Template

Page 8 of 30

Study number: 1484.0014

Document number: <insert>

Protocol date: 05-04-2023	Study number: 1484.0014	Version/Revision: V1.0	Version/Revision date:
Title of study:	Characterization of patients with Geographic Atrophy (GA)		
Rationale and background:	
There are many unknowns regarding the natural history of patients with GA, and limited data on the natural history of the disease. Recent results, presented in 2021 [1] [REDACTED] developed for the treatment of GA found a substantial number of patients with exudative choroidal neovascularization (classified as wAMD throughout the protocol) in the fellow eye or converting to eCNV in the study eye during the studies. These data might have affected the [REDACTED], and this population of patients may potentially impact the planned activities of BI. In [REDACTED] clinical trial, a high rate of conversion in the study eye occurred. This high rate of conversion may be influenced by the proportion of patients with wAMD present in the fellow eye. This project aims to provide clarity on the proportion of patients in the real world with GA, eCNV and focuses on both the study eye and fellow eye conversion rates, while also describing functional and imaging results, as well as treatment patterns.
		
Research question and objectives:	
This study aims to quantify and describe patients with a GA diagnosis in one eye, and progression in the study eye and the fellow eye to wAMD, or to GA (in the fellow eye), and the associated treatment journey.
		
Study design:	
This is an observational study, using existing data; The [REDACTED] Database.
		
Population:	
Patients attending a retina specialist, contributing to the [REDACTED] Database. Patients will be identified in the database from January 1, 2015, to April 30, 2023.
 
From those, our study population will be patients ≥ 50 years with a GA diagnosis in at least one eye will be eligible for this study.
 
The study period was selected to be able to identify patients with GA using the ICD-10 codes introduced in that year. The period from January 2015 until October 1st, 2015 will be used to identify patients diagnosed with ICD-9 codes and further classify them as new cases or patients with an previous diagnoses.
		
Variables:	
A primary outcome variable is visual acuity (VA), reported using converted Early Treatment Diabetic Retinopathy Study (ETDRS) letters.
 
[REDACTED]
 
[REDACTED]
 
[REDACTED]
 
Demographic characteristics – including age, gender, patient history, visit history
 
Clinical Characteristics – including ocular comorbidities, lens status, systemic conditions
		
Data sources:	
The [REDACTED] database consists of de-identified Electronic Health Records from a geographically diverse panel of 360+ United States based private retinal specialists contributing data from 70+ practices. Over the datasets entire history, there have been about 2 million patients and about 13 million patient visits.
		

BOEHRINGER INGELHEIM Group of Companies

NIS Protocol Template

Page 9 of 30

Study number: 1484.0014

Document number: <insert>

Study size:	
All patients available in the database and meeting the study criteria will be included.
 
The [REDACTED] includes approximately 400,000 patient eyes diagnosed with dry AMD, and around 70,000 patients diagnosed with GA during the study period. After the initial feasibility analysis, it is expected, given the study criteria, that there will be around 100,000 eyes included. However, this number might change in the final analysis.
									
Data analysis:	
In this study, both patients and eyes will be considered as the analysis unit. Baseline characteristics will be summarized using descriptive statistics. For continuous variables, the mean, standard deviation, median and range will be presented. For categorical variables frequency and proportion will be used. Variables are identified and calculated at the index diagnosis and throughout the follow-up period for primary outcomes like VA.
 
In the progression analysis, the population will be restricted to patients with a minimum follow-up time (i.e. multiple visits at least one year apart, at least two years), or patients with valid VA reading at the index diagnosis and a second follow-up timepoint. [REDACTED]
 
The analysis of incident and prevalent calculations will use as the denominator, all patients referred to the retinal specialist. The proportion of patients with a GA diagnosis referred to the retinal specialist will be put into perspective by comparing to other conditions, such as proportion of patients referred to the retinal specialist with a diabetic macular edema (DME) diagnosis, or with a diabetic retinopathy (DR) diagnosis etc. Additionally, extrapolations will be done to approximate to a population-based estimate.
									
Milestones:	
 
 Start of data collection	05/2023		
 
 End of data collection	06/2023		
 
 Final report of study results	06/2023		
 
	Start of data collection	05/2023		End of data collection	06/2023		Final report of study results	06/2023	
Start of data collection	05/2023									
End of data collection	06/2023									
Final report of study results	06/2023									

5. AMENDMENTS AND UPDATES

None

BOEHRINGER INGELHEIM Group of Companies**NIS Protocol Template****Study number: 1484.0014****Page 10 of 30****Document number: <insert>****6. MILESTONES**

Milestone	Planned Date
IRB/IEC approval	NA
Start of data collection	05/2023
End of data collection	06/2023
Registration in the EU PAS register	NA
Final report of study results	06/2023

7. RATIONALE AND BACKGROUND

GA is the late-stage form of dry age-related macular degeneration (AMD) and responsible for 10-20% of the legally blind cases. Currently, there is only one treatment for GA available for patients, [REDACTED] is not approved by EMA yet and therefore not available for patients in Europe. Patients with wet AMD (wAMD), another advanced form of AMD, can be treated with Anti-VEGF treatment.

Presently, Boehringer Ingelheim (BI) is developing potential treatments for the target population of patients with GA secondary to AMD [REDACTED]

There are many unknowns regarding the natural history of patients with GA, and limited data on the prevalence, incidence, and progression of the disease. Recent results from clinical trials developing treatments for GA [REDACTED] found a substantial number of patients with wAMD in the fellow eye or converting to wAMD (20 to 40%) [REDACTED]

[REDACTED] the [REDACTED] a high rate of conversion to wAMD in the study eye occurred. This high rate of conversion may be influenced by the proportion of patients with wAMD present in the fellow eye. This project aims to provide clarity on the proportion of patients in the real world, with GA, wAMD in both study and fellow eyes, and the conversion rates, describing also functional and imaging results and treatment patterns.

BOEHRINGER INGELHEIM Group of Companies

NIS Protocol Template

Page 11 of 30

Study number: 1484.0014

Document number: <insert>

8. RESEARCH QUESTION AND OBJECTIVES

Research Question

To quantify and describe patients with a GA diagnosis in at least one eye. [REDACTED]

Primary objectives

To describe the characteristics* of patients with GA in at least one eye.

To describe characteristics* of the study eye and the fellow eye, at index diagnosis

To evaluate and characterize the progression of newly diagnosed patients with GA during each year for 5-year follow-up period. In particular, to describe patients' characteristics, study eye and the fellow eye characteristics over the 5-years follow up. [REDACTED]

Secondary objectives

To determine the first time occurrence of GA in the study eye, during the study period.

To determine the proportion of patients with GA in the study eye, over the study period.

To compare the GA first time occurrence and the proportion of GA, relative to other retinal conditions, and relative to proportion of retinal specialist contributing to [REDACTED] and the overall US retinal specialist.

To evaluate patients' management (i.e. patients visits and procedures) over the study period.

To describe [REDACTED]

the overall GA population.

9. RESEARCH METHODS

9.1 STUDY DESIGN

This is an observational cohort study based on existing data.

BOEHRINGER INGELHEIM Group of Companies**NIS Protocol Template****Study number: 1484.0014****Page 12 of 30****Document number: <insert>****9.1.1 Study population**

Study inclusion criteria: All patients ≥ 50 years, with a GA diagnosis in at least one eye, including in the [REDACTED] database identified during the study period (January 2015 to April 2023).

Exclusion criteria: Patients without the information of laterality will be excluded.

No other exclusion criteria are applied for the identification of the study population and description of the patients and eye at baseline.

Additional note:

For certain analysis the patient population will be restricted to those with at least 12, 24, 36, 48, or 60 months of history following diagnosis of GA. For the analysis requiring a VA reading, a restriction to those patients with valid VA readings at the index diagnosis and the respective follow-up times will be applied.

For analysis estimating the size of the GA population relative to other retinal diseases, the same timeframe requirements that the study population will be applied. In this population, any patient in the database will be eligible, and the diagnosis of DME, DR or other conditions may be used for subgroup comparisons.

Primary Disease Definitions

In the [REDACTED] Database, retinal and other diseases are identified using the International Classification of Diseases (ICD), Tenth Revision, Clinical Modification. ICD 10 codes were launched in the USA in October 2015, and are the only version of ICD codes with adequate descriptions of GA and dry AMD severity. As such, only ICD 10 codes will be analyzed in this study and the study period defined above is directly related to the launch of ICD 10 plus a small buffer allowing for physician familiarity.

These codes are entered by the physician at patient visit, with an associated laterality. This, along with the ICD 10 laterality is used in combination to confirm in which eye the disease is occurring. For this study, a patient eye will be considered to have the study disease so long as there is an accompanying ICD code. The primary study diseases to be analyzed are dry AMD, GA and wAMD, and will be identified using the ICD codes in Table 1 below.

Table 1. Study disease definitions-codes.

Study Disease Definitions			
	Dry AMD*	Dry AMD with GA*	wAMD*
ICD 10	H35.311X, H35.312X, H35.313X, H35.319X	H35.3113, H35.3114, H35.3123, H35.3124, H35.3133, H35.3134, H35.3193, H35.3194	H35.321X, H35.322X, H35.323X, H35.329X
ICD 9 (2015 only)	362.51	N/A	362.52

*a comprehensive list of all AMD ICD codes is included in the Appendix

BOEHRINGER INGELHEIM Group of Companies**NIS Protocol Template****Study number: 1484.0014****Page 13 of 30****Document number: <insert>**

Patients could have simultaneously a diagnosis of wAMD and GA in the same eye. If both conditions are present, wAMD will be described as part of the comorbidities of the study or fellow eye. Patients could also have other ocular comorbidities affecting VA (section 9.3.3), those will be described and for the progression analysis will be analyzed separately.

For the follow-up analysis in the study eye or fellow eye, results will be described for all GA patients, patients with GA and wAMD, and patients with patients with GA only (without wAMD or other ocular comorbidities).

As the progression analysis tracking multiple different metrics across 2 eyes, it will be conducted at the patient level. Bilateral AMD disease is quite common (and will be identified), therefore the following methodology will be used to identify the 'Study' (primary) eye and the 'Fellow' (secondary) eye:

Study Eye – The first study eye in patient history identified with GA in the [REDACTED] database. GA is the only identifying disease in this case, and wAMD or dry AMD (without GA) in the study eye is not taken into account for study eye definition. If patients are bilaterally diagnosed, the study eye will be selected at random.

Fellow Eye – is defined as the other eye in a patient having their study eye diagnosed with GA. The fellow eye can have dry AMD, wAMD, GA or other retinal conditions. The fellow eye will be followed for progression purposes throughout the study.

Disease Status

Patient eyes will be identified at every visit throughout the study period to estimate the first time occurrence of GA and to estimate the proportion of patient with the disease over the years of the study period. Each visit will be classified as either an incident or a prevalent visit, defined below:

Incident visit – The first visit in patient eye history identified with GA in the [REDACTED] database. This timepoint also acts as each patients' index diagnosis. The incident visit may only occur once and contribute to one calendar year.

Prevalent visit – all visits following the incident visit in patient eye history while identified with GA in the [REDACTED] database. Prevalent visits may occur year after year throughout the patients' journey.

Study period

Patients will be identified from January, 2015 to April, 2023.

Selection period: Eligible patients must have at least one GA diagnosis between October 2015 and April 2023. The date of the first GA diagnosis will be considered as index date. For all follow up analysis, eligible patient eyes should be divided in those with at least 12, 24, 36, 48 and 60+ months of follow up. follow up requires multiple visits spanning over the outlined durations and total follow up is defined as the time between incident diagnosis and the final visit in the dataset.

BOEHRINGER INGELHEIM Group of Companies**NIS Protocol Template****Page 14 of 30****Study number: 1484.0014****Document number: <insert>**

Follow-up period: up to 60-month period following the index diagnosis date of GA (exploratory follow-up of 1, 2, 3, 4, 5 years may be run as cutoff points)

Pre-selection period: January 2015-September 2015. This period will be used to identify patients who have dry AMD using ICD9 coding, and will help to assign patients into the incidence or prevalence status.

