9.3 VARIABLES

9.3.1 Exposures

Study Treatments

The treatment variables below are identified at the patient eye level and will be used to describe the treatment patterns throughout the analysis. These treatment variables will be analyzed throughout the entire study period. Each treatment type can only occur once per patient eye visit and will be identified at every distinct visit where the following codes are present. Treatment must contain both the Current Procedural Terminology (CPT) codes for intravitreal injection and the J-codes specifying the study treatment (Table 2).

Though not common, it is possible for multiple different treatment types to occur on the same day, in which case both treatments would be captured for analysis i.e., a patient could get a laser and an injection at the same visit.

Table 2. Study Treatment Definitions

Study Treatment Definitions		
Treatment	CPT Code	
		[REDACTED]
		[REDACTED], C9214, C9257, Q9977
		Eylea- J0178, C9291, Q2046
		Lucentis-J2778, C9233
		Beovu- J0179

BOEHRINGER INGELHEIM Group of Companies

NIS Protocol Template

Study number: 1484.0014

Page 16 of 30

Document number: <insert>

		Susvimo – C9093, J2779 Byooviz- Q5124 Vabysmo- J2777, C9097 Cimerli- C9097, Q5128
Corticosteroids	Intravitreal Injection – 67028	Ozurdex-J7312 Triamcinolone-J3300, J3301 Iluvien-J7313 Yutiq-J7314
Laser	Focal Grid Laser- 67210 Panretinal Photocoagulation- 67228	Not Applicable
C3 Inhibitor	[REDACTED]	J3490, C9399

[REDACTED] will also accept an incoming procedure medication that is associated to an [REDACTED]
[REDACTED]
[REDACTED]

9.3.2 **Outcomes**9.3.2.1 Primary outcomes

- [REDACTED]

This study will evaluate the disease progression over time. The main progression endpoints will be for the study eye, [REDACTED], changes in the GA lesion location, changes in the VA or changes in the size of the GA lesion. For the fellow eye the progression endpoints will also include the developing of GA.

*Please see Table 1, that includes the disease definitions (dry AMD, GA, and wAMD) based on ICD codes.

- **Position of GA lesion will be assessed over time.** The position of GA lesion will be defined using ICD 10 coding defined below. Any change in location status will be identified as progression of GA

Study Disease Definitions-lesion location		
	GA without Subfoveal Involvement	GA with Subfoveal Involvement
ICD 10	H35.3113, H35.3123, H35.3133, H35.3193,	H35.3114, H35.3124, H35.3134, H35.3194

BOEHRINGER INGELHEIM Group of Companies

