- Follow up reading at Month 24, 36, 60: +/- 60 days

Incidence (new cases) and prevalence of GA will be captured, based on the ICD 10 diagnosis codes. On a calendar basis, all newly diagnosed patients will be identified and count as incident patients. Patients with a previous diagnosis of GA in the past years (with respect to a given calendar year), will be counted as prevalent cases during that calendar year.

The yearly counts of newly diagnosed or prevalent cases, will help to understand the progression of the overall disease.

BOEHRINGER INGELHEIM Group of Companies**NIS Protocol Template****Study number: 1484.0014****Page 18 of 30****Document number: <insert>****9.3.2.2 Secondary outcomes****• Retinal Disease Related HCRU Outcomes**

Change in physician care over time will be evaluated from the incident date of GA, and assessed on a yearly basis in order to assess if physician habits have changed over time, particularly following September 2021 and additionally following [REDACTED].

Patient visits: A patient visit (or encounter) is identified in the database any time a patient visits one of the panel physicians. Since the [REDACTED] database consists only of private practicing retina specialists, these are the only types of visits analyzed in the study.

If a patient visits the physician at a hospital, institution, or has an emergency room admission, the event will not be captured. For all patient visits, it is assumed that both eyes are being seen/assessed even in the primary visit reason is for one particular eye. In this sense, all visits will contribute to both eyes and any outcomes at these visits will be available for assessment.

Treatments: The documentation includes **all treatments** including injections, laser treatments, and other procedures. The type of diagnostic procedure done, and the results of these diagnostics are also recorded for most encounters. For any visit, it is assumed that both eyes are being seen, even if only one eye receives any treatment.

Other medical procedures: for example, cataracts removal, eye lid (ptosis correction), etc.

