9.3.3 Covariates

9.3.3.1 Demographic Characteristics: The demographic variables below are identified at the patient eye level and will be used to describe the demographic characteristics throughout the analysis. These demographic characteristics will be analyzed at the index diagnosis, unless specified elsewhere.

Age: will be calculated based on DOB from index diagnosis (incident visit).

Sex: identified at index diagnosis, or other visits if not specified.

Diagnosis year: Identified as the calendar year of the index diagnosis.

Months of History: will be defined as the time from index diagnosis to their last record in the database.

Incident Visit: The first visit in the database where one of the study diseases is identified, per eye. This may include Dry AMD, GA and/or wAMD. At incident visits all clinical characteristics, ocular comorbidities, etc. will be also captured.

Prevalent Visit: The first visit during a time period of interest where one of the study diseases is identified, per eye. This may include Dry AMD, GA and/or wAMD. This visit must not be the first diagnosis in the entire patient history. At prevalent visits changes in the clinical

BOEHRINGER INGELHEIM Group of Companies**NIS Protocol Template****Study number: 1484.0014****Page 19 of 30****Document number: <insert>**

characteristics, ocular comorbidities will be captured and described based on the first prevalent visit per calendar year.

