9.7 DATA ANALYSIS

9.7.1 Main analysis

All analysis will be performed individually on the study population(s). All study results will be provided in tables, and key findings will be highlighted and summarized. The analyses will be conducted at both the patient and patient eye level, as appropriate.

Analysis for objective:

To describe the characteristics* of patients with GA in at least one eye.

To describe characteristics* of the study eye and the fellow eye, at index diagnosis (i.e., proportion of patients with GA in the fellow eye, [REDACTED]

All demographics, and clinical characteristics will be summarized at the index diagnosis date (first diagnosis of GA in the study eye).

Characteristics include demographics, comorbidities, comedications (patient level).

And at eye level; AMD, GA, eCNV, other ocular comorbidities, functional parameters i.e. VA. As well as treatments administered prior to or at index.

Summary will include descriptive statistics; continuous variables will consist of mean (SD) and median (IQR) while categorical variables will be described using frequency and proportion. Absolute numbers (n) of the variables (either yes or patients as appropriate) will be always included in the description of the results.

Analysis for objective:

To evaluate and characterize the progression of newly diagnosed patients with GA during a 5-year follow-up period. To describe patients' characteristics, study eye and the fellow eye characteristics, [REDACTED]

[REDACTED] or progression of the GA lesion in the study eye. To evaluate changes in VA, to evaluate changes in the lesion location, and lesion size (where available).

Patients with GA will be analyzed as an overall group. Subgroups will be also analyzed separately: only GA, GA and wAMD, GA and other comorbidities, and bilateral GA at baseline.

Ocular comorbidities will also be tracked longitudinally (yearly) from index date (GA diagnosis in the database) to better understand the disease journey.

Disease progression will be analyzed at both patient and each individual eye level.

Progression to dry AMD, to GA and to wAMD will be assessed independently using time to event analysis, and also the rate of progression that is seen in the study (2nd, 3rd, 4th, and 5th) years. Bilateral GA eyes at baseline will be evaluated for progression to wAMD

BOEHRINGER INGELHEIM Group of Companies**NIS Protocol Template****Study number: 1484.0014****Page 23 of 30****Document number: <insert>**

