9.8 QUALITY CONTROL

The EMR information [REDACTED] receives is loaded into the input database unchanged. The incoming data are subject to quality control steps to ensure all the expected data are received and files are complete and readable. Changes in historic data are labeled as such and both original and modified values retained.

Input data are transformed into the operational database through a quality assurance process to ensure the validity of each data point. Metrics are tracked longitudinally to ensure logical consistency visits over visit, and are required to fall within specified limits (thresholds have been set using clinical insight from active retina specialists). Incidental Personal Health Information (PHI) contained in text fields are removed, information in text strings that contain multiple data elements are broken down into separate analyzable and standardized cells. [REDACTED]
[REDACTED]

All data shared with BI will be at an aggregated stage, and will be fully de-identified and HIPAA compliant

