As an overall limitation of the dataset, Data in the EHR is recorded by the physician or scribe under the direction of the physician. Physicians do not tend to enter data that is not directly relevant to the patient's current condition and tend not to enter null information. There is no real time validation of the information entered during the encounter either in terms of completeness or accuracy. However, ██████████ works extensively with the physicians providing analysis of their own data. As such, this is a crucial step in the data validation process, as physicians analyzing their own data over the years has provided insights on better coding, data entry and completeness. This limitation will affect the covariates related to comorbidities outside of retina. The current workaround is to use the systemic medications list provided to identify the treatment of these comorbidities (diabetes, hypertension etc.). However, this field also comes with its own limitation of relying on the physician/patient to provide an accurate summary of each patient's medication list.

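### In the visible text a single unconfirmed ICD code counts as conversion to wAMD, so false conversions can build up with visits, and no planned analysis shows how much this matters

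*Combined protocol and SAP*

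**What the plan says.** Section 9.1.1 (Primary Disease Definitions) covers dry AMD, GA and wAMD with one rule: "For this study, a patient eye will be considered to have the study disease so long as there is an accompanying ICD code". Section 9.3.3.1 dates disease at "The first visit in the database where one of the study diseases is identified, per eye", and states that this can be wAMD. The progression endpoints in section 9.3.2.1 refer back to the code list: "Please see Table 1, that includes the disease definitions (dry AMD, GA, and wAMD) based on ICD codes". Section 9.7.1 adds: "Progression to dry AMD, to GA and to wAMD will be assessed independently using time to event analysis".

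On checking, section 9.1.1 combines the physician's laterality entry with the laterality in the ICD-10 code, which "is used in combination to confirm in which eye the disease is occurring". That confirms the eye, not the diagnosis. Section 9.8 describes a general check: "Metrics are tracked longitudinally to ensure logical consistency visits over visit". Section 9.9 concedes: "There is no real time validation of the information entered during the encounter either in terms of completeness or accuracy".

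The visible text contains no second-code rule, no requirement for treatment or fluid findings to support a wAMD code, and no sensitivity analysis on the wAMD definition. By contrast, section 9.3.1 accepts an injection treatment only when a CPT code and a J-code are both present.

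**The concern.** In a first-event analysis with an irreversible event, each further visit adds a chance of a false conversion and none can remove one. The error therefore depends on how often the eye is observed as well as on how accurate the coding is.

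This touches the question behind the study. Section 7 suggests that high study-eye conversion may be influenced by wAMD in the fellow eye. Patients treated in the fellow eye are likely to be seen more often, and section 9.3.2.2 counts every visit for both eyes: "it is assumed that both eyes are being seen/assessed". More visits mean more chances of a stray code in the study eye, so the rule could produce part of the association under study. The same dependence could enter the follow-up strata in section 9.2.1 and the progressor comparisons and logistic model in section 9.7.1. Section 9.9 does not discuss false-positive wAMD codes.

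**Working it through.** The documents state no conversion rate for this database and no coding error rate, so there is no plan figure to reproduce. What follows is a range under stated assumptions.

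**Inputs from the protocol**
- Section 9.2.1: 13 million visits and 2 million patients, each given as a minimum. 13 / 2 = 6.5 visits per patient, across all conditions and the database's lifetime. This is a rough proxy, rounded up to 7.
- Section 9.5: 72,718 GA patients, mean follow-up 22 months, 20,503 with visits after 3 years. 20,503 / 72,718 = 28%, so long follow-up applies to a minority.

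**Assumptions**
- q = probability of a false wAMD code per visit: 0.1%, 0.5% or 1%, independent across visits.
- p = true cumulative conversion, taken as 20%, with all true converters coded.
- n = 7 visits, or 20 for long follow-up.

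**Formulas**
- False-conversion risk in a true non-converter: F = 1 − (1 − q)^n.
- Observed conversion: p + (1 − p)F. False events arise only among non-converters.

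| q | F, n = 7 | observed, n = 7 | F, n = 20 | observed, n = 20 |
|---|---|---|---|---|
| 0.1% | 0.70% | 20.6% | 2.0% | 21.6% |
| 0.5% | 3.4% | 22.8% | 9.5% | 27.6% |
| 1% | 6.8% | 25.4% | 18.2% | 34.6% |

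For example, with q = 0.5% and n = 7: F = 1 − 0.995^7 = 0.0345, and 0.20 + 0.80 × 0.0345 = 0.228.

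**Differential visits (all inputs assumed).** Let true conversion be 10% in both groups and q = 0.3%, with 24 visits in one group and 6 in the other.
- 24 visits: F = 1 − 0.997^24 = 0.070, so observed conversion is 0.10 + 0.90 × 0.070 = 16.3%.
- 6 visits: F = 1 − 0.997^6 = 0.018, so observed conversion is 0.10 + 0.90 × 0.018 = 11.6%.
- The ratio is about 1.4, with no true difference.

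**Opposite direction.** With p = 20%, q = 0.5% and n = 7, the excess is 0.80 × 0.0345 = 0.0276. It would be cancelled if 0.0276 / 0.20 = 13.8% of true converters were never coded in the database.

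**What confirmation does.** Under a rule needing two false codes at separate visits, F at 7 visits falls to 0.002%, 0.05% and 0.20% for the three values of q. At q = 0.5% the observed rate returns to 20.0%. The price is missed true events. With two visits after conversion and 80% coding per visit, the one-code rule misses 0.2² = 4% and the two-code rule misses 1 − 0.8² = 36%. With one visit after conversion, a second code is impossible.

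**The case against.** A reader might infer that the conversion rate will be materially inflated and that the main definition must be replaced. The documents do not support that.

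- **Size.** No miscoding rate is given. Codes are entered at the visit by retina specialists, and nothing says that provisional wAMD codes are used. At q = 0.1% and 7 visits the shift is 0.6 percentage points. If an erroneous code is carried forward from visit to visit, accumulation is slower than modelled.
- **Safeguards.** Patients without laterality are excluded, laterality is cross-checked, and sections 9.8 and 9.9 describe consistency checks and physicians' review of their own data. These reduce the exposure, but none is a stated rule for confirming a wAMD diagnosis.
- **Net direction.** Section 9.9 says that care at other practices is not captured. Missed conversions lower the rate, so net inflation is not established.
- **Benchmark.** It is tempting to set the bias against the 20 to 40% in section 7. That figure covers wAMD in the fellow eye or conversion, and the visible text plans no formal comparison with it.
- **Hidden text.** The first primary-outcome bullet and part of the endpoint sentence in section 9.3.2.1 are redacted, and the codes workbook named in Annex 1 is not available here. A wAMD-specific rule could sit in either.
- **Replacing the definition.** Confirmation depends on later visits and so favours patients seen often. Using anti-VEGF to confirm would also build treatment into the case definition, although the research question asks how many converters are treated.

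These points stand as limits on size, direction and choice of main definition. They do not remove the mechanism or show that it is negligible.

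**Conclusion.** The point holds as a gap in robustness. On the visible text, one unconfirmed code makes a wAMD event, and the false-positive risk can only rise with visits. Around the database-average visit count, a true 20% would read between 20.6% and 25.4% for q from 0.1% to 1%; at 20 visits the range is 21.6% to 34.6%. These figures rest on assumed error rates, independence between visits, complete coding of true converters and a database-wide visit proxy. The potential distortion of the fellow-eye comparison is at least as important as the shift in the overall rate. The single-code rule is a defensible choice for the main analysis of a descriptive study. What is missing is an analysis showing whether the result depends on it. This is a cheap improvement, not a fatal flaw.

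**What to change.** Keep the single-code definition as the main analysis, and add the following to section 9.7.1.

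1. A prespecified sensitivity analysis of wAMD conversion that requires same-eye corroboration within a fixed window: a second wAMD code at a later visit, a recorded fluid finding, or anti-VEGF treatment in that eye. Date the event at the first code.
2. The share of single-code events confirmed, among eyes with at least one later visit in the window, overall and by fellow-eye wAMD status.
3. A statement that the anti-VEGF route is left out when the proportion of converters treated is reported.

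If the redacted text or the codes workbook already holds a confirmation rule, section 9.1.1 should refer to it.

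Cost: one code-level rule on fields already held (treatment codes in section 9.3.1, fluid status in section 9.4) and one table. Some true late conversions cannot be confirmed, free-text fluid data are incomplete, and carried-forward errors can pass the second-code route. Reporting the single-code and confirmed results side by side shows how far they differ; the gap contains unconfirmable true events as well as false ones.
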